7.6.1 Deaths

Deaths will be summarized by tumor group:

- All deaths, reasons for death

Deaths within 30 days and 100 days of last dose received, reasons for deathBy-subject listing of deaths will be provided for the All Enrolled Subjects population.

7.6.2 Serious Adverse Events

Serious adverse events will be summarized by tumor group:

- Overall summary of SAEs by worst CTC grade (grade 1, 2, 3, 4, 5, unknown) presented by SOC/PT using the 30-day and repeated using the 100-daysafety window
- Overall summary of SAEs by worst CTC grade (any grade, grade 3-4, grade 5) presented by SOC/PT using the 30-day and repeated using the 100-day safety window and for AEs with extended follow-up. This table will be restricted to events with incidence greater or equal to 1% in any tumor group.
- Overall summary of drug-related SAEs by worst CTC grade (any grade, grade 3-4, grade 5) presented by SOC/PT using the 30-day and repeated using the 100-day safety window and AEs with extended follow-up

By-subject SAE listing will be provided for the All Enrolled Subjects population.

7.6.3 Adverse Events Leading to Discontinuation of Study Therapy

AEs leading to discontinuation will be summarized by tumor group:

- Overall summary of AEs leading to discontinuation by worst CTC grade (grade 1, 2, 3, 4, 5, unknown) presented by SOC/PT
- Overall summary of AEs leading to discontinuation by worst CTC grade (any grade, grade 3-4, grade 5) presented by SOC/PT
- Overall summary of drug-related AEs leading to discontinuation by worst CTC grade (grade 1, 2, 3, 4, 5, unknown) presented by SOC/PT
- Overall summary of drug-related AEs leading to discontinuation by worst CTC grade (any grade, grade 3-4, grade 5) presented by SOC/PT

The analysis will be conducted using the 30-day and repeated using the 100-day safety window.

By-subject AEs leading to discontinuation listing will be provided.

7.6.4 Adverse Events Leading to Dose Modification

AEs leading to dose delay/interruptions will be summarized for each tumor group:

- Overall summary of AEs leading to dose delay/reduced by worst CTC grade (grade 1, 2, 3, 4, 5, unknown) presented by SOC/PT

The analysis will be conducted using the 30-day and repeated using the 100-day safety window.

By-subject AEs leading to dose delay/reduced listing will be provided.

7.6.5 Adverse Events

Adverse events will be summarized by tumor group:

- Overall summary of any AEs by worst CTC grade (grade 1, 2, 3, 4, 5, unknown) presented by SOC/PT using the 30-day and repeated using the 100-day safety window
- Overall summary of any AEs by worst CTC grade (any grade, grade 3-4, grade 5) presented by SOC/PT using the 30-day and repeated using the 100-day safety window and for AEs with extended follow-up. This table will be restricted to events with an incidence greater or equal to 5% in any tumor group.
- Overall summary of drug-related AEs by worst CTC grade (any grade, grade 3-4, grade 5) presented by SOC/PT using the 30-day and repeated using the 100-day safety window and for AEs with extended follow-up
- Overall summary of any non-serious AEs presented by SOC/PT using the 30-day and repeated using the 100-day safety window. This table will be restricted to events with an incidence greater or equal to 5% in any tumor group.

Summary of late emergent drug-related AEs by worst CTC grade presented by SOC/PT for AEs reported beyond 100 days after last dose of study therapy

By-subject AE listing will be provided.

7.6.6 Select Adverse Events

Unless otherwise specified, analyses will be performed by select AE category.

7.6.6.1 Incidence of Select AE

Select AEs (see Table 11-3 of CA209 Core Safety SAP) will be summarized by tumor group for each category/subcategory:

- Overall summary of any select AEs by worst CTC grade presented by Category or Subcategory/PT (any grade, grade 3-4, grade 5)
- Overall summary of drug-related select AEs by worst CTC grade presented by Category or Subcategory / PT (any grade, grade 3-4, grade 5)
- Overall summary of any serious select AEs by worst CTC grade presented by Category or Subcategory /PT (any grade, grade 3-4, grade 5)

- Overall summary of drug-related serious select AEs by worst CTC grade presented by Category or Subcategory /PT (any grade, grade 3-4, grade 5)
- Overall summary of any select AEs leading to discontinuation by worst CTC grade presented by Category or Subcategory /PT (any grade, grade 3-4, grade 5)
- Overall summary of drug-related select AEs leading to discontinuation by worst CTC grade presented by Category or Subcategory /PT (any grade, grade 3-4, grade 5)

The analyses will be conducted using the 30-day and repeated using the 100-day safety window and/or extended follow-up. Refer to CA209 Core Safety DPP for details,

By-subject select AE listing will be provided.

7.6.6.2 Time to Onset/Resolution of Select AE

Time-to onset, time-to resolution and time-to resolution where immune modulating medication was initiated will be analyzed for each specific category/subcategory:

- Summary of time to onset of drug-related select AEs by category for treated subjects who experienced at least one drug- related select adverse event from the category
- Summary of time to resolution of drug-related select AEs by category for treated subjects who experienced at least one drug- related select adverse event from the category
- Summary of time to resolution of drug-related select AEs where immune modulating medication was initiated by category for treated subjects who experienced at least one drug- related select adverse event from the category

7.6.7 Immune Modulating Medication

The percentage of subjects who received immune modulating concomitant medication for

- management of adverse event
- premedication
- other use

will be reported separately for each tumor group (percentages of treated subjects by medication class and generic term).

For each category/subcategory of select AEs (see Table 11-3 of CA209 Core Safety SAP), the following will be reported for each tumor group:

- Percentage of subjects who received immune modulating concomitant medication for management of any select AE in the category among subjects who experienced at least one select adverse event in the category/subcategory.
- The total medication treatment duration, duration of high dose of corticosteroid and tapering duration (summary statistics)

These analyses will be performed on any select AEs, drug-related select AEs, grade 3-5 select AEs and drug-related select AEs.

Total duration of all immune modulating medications (excluding overlaps) given for select AEs management will be reported.

The analysis will be conducted using the 30-day and repeated using the 100-day safety window, if applicable. Refer to CA209 Core Safety DPP for details,

7.6.8 *Multiple Events*

The following summary tables will be provided:

- A table showing the total number and rate (exposure adjusted) of occurrences for all AEs
- A table showing the total number and rate (exposure adjusted) of occurrences for AEs occurring in at least 5% of the subjects treated in any treatment group

In addition, the rate (exposure adjusted) and its 95% CI evaluated for different time intervals will be displayed graphically for each tumor group. This analysis will be limited to the rate of all AEs and all drug-related AEs. Refer to CA209 Core Safety DPP for details,

Listing displaying the unique instances of all AEs, i.e., after duplicates have been eliminated and overlapping and contiguous occurrences of the same event (i.e. same PT) have been collapsed will be provided. No formal comparisons will be made between tumor groups.

7.6.9 *Clinical Laboratory Evaluations*

Clinical laboratory parameters (hematology, serum chemistry and electrolytes) will be evaluated. Laboratory tests will be graded using the NCI Common Terminology Criteria, version 4.0. Clinical laboratory data will be first analyzed using International System of Units (SI). Analyses will be repeated using US conventional units..

7.6.9.1 *Hematology*

The following will be summarized by tumor group as worst CTC grade on-treatment per subject and as shift table of worst on-treatment CTC grade compared to baseline CTC grade per subject: hemoglobin (HB), platelets, white blood counts (WBC), absolute neutrophils count (ANC) and lymphocyte count (LYMPH).

The analyses will be conducted using the 300-day safety window and repeated using the 100-day safety window.

A by-subject listing of these laboratory parameters will be provided.

7.6.9.2 *Serum Chemistry*

The following will be summarized by tumor group as worst CTC grade on-treatment per subject and as shift table of worst on-treatment CTC grade compared to baseline CTC grade per subject: ALT, AST, alkaline phosphatase (ALP), total bilirubin and creatinine.

The analyses will be conducted using the 300-day safety window and repeated using the 100-day safety window.

A by-subject listing of these laboratory parameters will be provided.

7.6.9.3 *Electrolytes*

The following will be summarized by tumor group as worst CTC grade on-treatment per subject and as shift table of worst on-treatment CTC grade compared to baseline CTC grade per subject: sodium (high and low), potassium (high and low), calcium (high and low), magnesium (high and low).

The analyses will be conducted using the 30-day safety window and repeated using the 100-day safety window.

A by-subject listing of these laboratory parameters will be provided.

7.6.9.4 *Abnormal Thyroid Function Test*

The number of subjects with the following laboratory abnormalities from on-treatment evaluations will be summarized by tumor group:

- TSH value $>$ ULN and
 - with baseline TSH value \leq ULN
 - at least one FT3/FT4 test value $<$ LLN
- TSH $<$ LLN and
 - with baseline TSH value \geq LLN
 - at least one FT3/FT4 test value $>$ ULN

The analyses will be conducted using the 30-day safety window and repeated using the 100-day safety window.

A by-subject listing of these specific abnormalities will be provided.

7.6.9.5 *Abnormal Hepatic Function Test*

The number of subjects with the following laboratory abnormalities from on-treatment evaluations will be summarized by tumor group:

- ALT or AST $>$ 3 x ULN, $>$ 5 x ULN, $>$ 10 x ULN and $>$ 20 x ULN
- Total bilirubin $>$ 2 x ULN

- Concurrent (within 1 day) ALT or AST $> 3 \times$ ULN and total bilirubin $> 2 \times$ ULN
- Concurrent (within 30 days) ALT or AST $> 3 \times$ ULN and total bilirubin $> 2 \times$ ULN

The following scatterplots will be produced for the following hepatic laboratory parameters:

- Total bilirubin peak vs. AST peak
- Total bilirubin peak vs. ALT peak

On-treatment peak total bilirubin and on-treatment peak AST/ALT may or may not happen on the same day of liver testing.

The analyses will be conducted using the 30-day safety window and repeated using the 100-day safety window.

A by-subject listing of these specific abnormalities will be provided.

7.6.10 *Vital Signs*

Vital signs parameters (systolic blood pressure [mmHg], diastolic blood pressure [mmHg], heart rate [bpm], respiratory rate [breaths/min] and body temperature [$^{\circ}$ C]) will be listed. Summaries of vital signs parameters and respective changes from baseline will be provided for each vital signs parameter by tumor group and study visit.

Subjects with vital signs outside of a pre-specified range will also be listed.

7.6.11 *ECOG Performance Status*

Summaries of ECOG performance will be provided by tumor group and study visit. A by-subject listing of ECOG will be provided.

Classification of ECOG performance status is provided in Table 7.6-12.

Table 7.6-12: ECOG PERFORMANCE STATUS

ECOG PERFORMANCE STATUS	
Grade	ECOG
0	Fully active, able to carry on all pre-disease performance without restriction
1	Restricted in physically strenuous activity but ambulatory and able to carry out work of a light or sedentary nature, e.g., light house work, office work
2	Ambulatory and capable of all self-care but unable to carry out any work activities. Up and about more than 50% of waking hours
3	Capable of only limited self-care, confined to bed or chair more than 50% of waking hours
4	Completely disabled. Cannot carry on any self-care. Totally confined to bed or chair

Table 7.6-12:

ECOG PERFORMANCE STATUS

ECOG PERFORMANCE STATUS	
5	Dead

7.6.12 *Pregnancy Testing*

By-subject listing of pregnancy tests results will be provided for all treated female subjects.

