Physical examinations are to be performed as clinically indicated. If there are any new or worsening clinically significant changes since the last exam, report changes on the appropriate non-serious or serious adverse event page.

On treatment local laboratory assessments are to be completed within 3 calendar days prior to dosing.

Additional measures, including non-study required laboratory tests, should be performed as clinically indicated or to comply with local regulations. Laboratory toxicities (eg, suspected drug induced liver enzyme evaluations) will be monitored during the follow-up phase via on site/local labs until all study drug related toxicities resolve, return to baseline, or are deemed irreversible.

If a subject shows pulmonary-related signs (hypoxia, fever) or symptoms (eg, dyspnea, cough, fever) consistent with possible pulmonary adverse events, the subject should be immediately evaluated to rule out pulmonary toxicity, according to the suspected pulmonary toxicity management algorithm in the BMS-936558 Nivolumab Investigator Brochure and [Appendix 3](#).

Some of the assessments referred to in this section may not be captured as data in the eCRF. They are intended to be used as safety monitoring by the treating physician. Additional testing or assessments may be performed as clinically necessary or where required by institutional or local regulations.

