6.1.2 Post Baseline Period

On-treatment AEs will be defined as AEs with an onset date and time on or after the date and time of the first dose of study treatment (or with an onset date on or after the day of first dose of study treatment if time is not collected or is missing). An AE will be counted as on-treatment if the event occurred within 30 days (or 100 days depending on analysis) (see Core Safety SAP), of the last dose of study treatment. No subtracting rule will be applied when an AE occurs both pre-treatment and post-treatment with the same preferred term and grade.

On-treatment evaluations (e.g., laboratory tests and vital signs) will be defined as evaluations taken after the day (and time, if collected and not missing) of first dose of study treatment. An evaluation will be counted as on-treatment if it occurred within 30 days (or 100 days depending on analysis) of the last dose of study treatment.

Late emergent drug-related AEs will be defined as drug-related AEs with an onset date greater than 100 days after the last dose of study treatment in subjects off study treatment.

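### SAP hematology and serum chemistry tables carry a 300-day window that conflicts with the SAP's own 30- or 100-day on-treatment definition, most likely a slip for 30

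*SAP*

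**What the plan says.** SAP 6.1.2 defines the post-baseline period. Laboratory tests are its named example: "On-treatment evaluations (e.g., laboratory tests and vital signs) will be defined as evaluations taken after the day" of first dose (and time, if collected). At the other end, an evaluation is "counted as on-treatment if it occurred within 30 days (or 100 days depending on analysis) of the last dose of study treatment". The same section classes as late emergent "drug-related AEs with an onset date greater than 100 days after the last dose of study treatment in subjects off study treatment".

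SAP 7.6.9.1 covers hemoglobin, platelets, WBC, ANC and lymphocytes. SAP 7.6.9.2 covers ALT, AST, ALP, total bilirubin and creatinine. Each asks for worst on-treatment grade per subject and a "shift table of worst on-treatment CTC grade compared to baseline CTC grade per subject". Each then sets its window with the same sentence: "The analyses will be conducted using the 300-day safety window and repeated using the 100-day safety window".

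The three laboratory sections that follow (7.6.9.3 electrolytes, 7.6.9.4 thyroid, 7.6.9.5 hepatic) use a sentence that differs only in the first figure: "The analyses will be conducted using the 30-day safety window and repeated using the 100-day safety window".

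The protocol determines which values can exist after the last dose. Table 5.1-4 schedules laboratory tests at X01 (Day 35 ± 7) and X02 (Day 100 ± 7), and none in survival follow-up. Protocol 5.3 adds that laboratory toxicities "will be monitored during the follow-up phase via on site/local labs until all study drug related toxicities resolve", return to baseline or are judged irreversible. It also says that some assessments in that section may not be captured in the eCRF.

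**The concern.** The window decides which values feed a worst-grade table, and 300 is neither of the two figures that the SAP's definition allows. A display cannot be on-treatment in the sense of 6.1.2 and also reach day 300. The text is operative, since 6.1.2 leaves the choice between 30 and 100 to the individual analysis and a programmer would look to 7.6.9.1 and 7.6.9.2 for the number.

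Two things are at stake if the figure is followed as written. Values drawn well after treatment would be labelled on-treatment toxicity, and neither 6.1.2 nor 7.6.9 excludes values taken after subsequent cancer therapy has started. In addition, the contrast between a 30-day and a 100-day table, which the other laboratory panels have, would be lost for the basic blood count and chemistry parameters.

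**Working it through.** There is no power or error-rate figure to reproduce. The check sets the windows side by side and then counts which draws each window admits.

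**Step 1: the windows.**

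| SAP section | Content | First window (days) | Repeat (days) |
|---|---|---|---|
| 6.1.2 | Definition of an on-treatment evaluation | 30 | or 100, by analysis |
| 7.6.9.1 | Hematology, 5 parameters | 300 | 100 |
| 7.6.9.2 | Serum chemistry, 5 parameters | 300 | 100 |
| 7.6.9.3 | Electrolytes | 30 | 100 |
| 7.6.9.4 | Thyroid | 30 | 100 |
| 7.6.9.5 | Hepatic thresholds | 30 | 100 |

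Parameters affected: 5 + 5 = 10. The excess is 300 − 30 = 270 days over the shorter limit (a factor of 300/30 = 10) and 300 − 100 = 200 days over the longer one (a factor of 3). Only in the two affected sections is the first window wider than its repeat. SAP 7.6.1 to 7.6.5, 7.6.6.1 and 7.6.7 also use 30 and 100 days. A 300-day window appears nowhere else in either document.

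**Step 2: internal consequences.** ALT, AST and total bilirubin would be on-treatment to day 300 in 7.6.9.2 but to day 30 in the first analysis of 7.6.9.5. A laboratory value on day 200, for example, would count as on-treatment, while a drug-related adverse event starting that day would be late emergent under 6.1.2.

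**Step 3: scheduled draws after last dose (Protocol Table 5.1-4).** X01 runs from 35 − 7 = day 28 to 35 + 7 = day 42. X02 runs from 100 − 7 = day 93 to 100 + 7 = day 107. The blood count and chemistry panel at these visits cover all 10 parameters.

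| Draw | 30-day table | 100-day table | 300-day table |
|---|---|---|---|
| X01, days 28 to 42 | days 28 to 30 only | all | all |
| X02, days 93 to 107 | none | days 93 to 100 | all |
| Unscheduled or local, days 108 to 300 | none | none | any that are recorded |

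On the nominal schedule a 30-day table admits 3 of the 15 possible X01 days. If treatment is discontinued more than 30 days after last dose, X01 may be tied to the discontinuation date instead. Its earliest day is then 31 − 7 = day 24, so a few more X01 draws could qualify; this does not change the picture.

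Against a 30-day table, the 300-day window therefore adds nearly all scheduled follow-up draws. Against the 100-day table, it adds X02 draws on days 101 to 107 and any recorded later value.

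**Step 4: direction of the effect.** Worst grade is a maximum. For a subject with values in each window, the worst grade to day 300 is at least the worst grade to day 100, which is at least the worst grade to day 30. Widening the window can leave a grade unchanged or raise it, never lower it. The documents give no data from which to estimate how often it would rise.

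**The case against.** The strongest reply is that this is an obvious slip that nobody would program. The sentence otherwise matches 7.6.9.3 to 7.6.9.5, the tables are labelled with a term that 6.1.2 defines, and SAP 7.6 follows a Core Safety SAP and a data presentation plan whenever appropriate. Those documents are not available here and may already fix the window. This makes literal programming less likely. It does not remove an explicit contrary instruction that appears twice in this SAP.

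The second reply is that little would change even if the text were followed. Scheduled tests end at about day 107. Later values come only from unscheduled or local follow-up, some of which may never reach the eCRF. Tests drawn to follow a known toxicity to resolution will often sit at or below a peak already recorded. This stands for the period after day 107. It does not answer the loss of the 30-day table, because X01 and X02 alone fill most of the difference.

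Three stronger readings are tempting, and the documents do not support them:

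- A reader might infer that the tables would be substantially inflated by toxicity out to day 300. The number of such values is unknown, and the eCRF sentence in Protocol 5.3 points to a small one.
- A reader might infer that all 30-day reporting of ALT, AST and bilirubin disappears. SAP 7.6.9.5 keeps 30-day threshold counts, concurrent elevations and peak scatterplots; only the worst-grade and shift formats lose their 30-day version.
- A reader might infer that every other safety display uses 30 days. SAP 7.6.6.2, 7.6.8, 7.6.10 and 7.6.11 state no 30-day window.

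**Conclusion.** The contradiction is real: two operative rules give a window that the SAP's own definition does not allow. It is most likely a typing error for 30, which is an inference from the paired 100-day repeat and the parallel sections.

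The consequence is conditional on literal programming. In that case all 10 parameters, in every tumor group, would have a first table that largely overlaps its 100-day repeat, and none would have a 30-day worst-grade or shift table. The 100-day repeats remain correctly specified. No efficacy analysis, stopping rule or cohort decision is touched.

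This rests on two assumptions: that the Core Safety SAP does not override the stated window, and that X01 and X02 laboratory results are recorded as scheduled. The point is a cheap specification error to correct before programming, and no threat to the trial's conclusions.

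**What to change.** In SAP 7.6.9.1 and 7.6.9.2, change 300-day to 30-day, so that both match 6.1.2 and 7.6.9.3 to 7.6.9.5. Check the figure against the Core Safety SAP first. If 300 was intended, give the reason and amend 6.1.2 so that the definition and the tables agree.

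The cost is one digit removed from each of two sentences. If the tables have already been programmed, confirm which window was used and rerun them if it was 300. Data collection does not change.

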8 CONVENTIONS

The following conventions may be used for imputing partial dates for analyses requiring dates:

For death dates, the following conventions will be used for imputing partial dates:

- If only the day of the month is missing, the 1st of the month will be used to replace the missing day. The imputed date will be compared to the last known date alive and the maximum will be considered as the death date.
- If the month or the year is missing, the death date will be imputed as the last known date alive
- If the date is completely missing but the reason for death is present the death date will be imputed as the last known date alive

For date of progression, the following conventions will be used for imputing partial dates:

- If only the day of the month is missing, the 1st of the month will be used to replace the missing day.
- If the day and month are missing or a date is completely missing, it will be considered as missing.

In cases where the date of death is present and complete, the imputed progression date will be compared to the date of death. The minimum of the imputed progression date and date of death will be considered as the date of progression.

For missing and partial adverse event onset dates, imputation will be performed using the Adverse Event Domain Requirements Specification⁵.

For missing and partial adverse event resolution dates, imputation will be performed as follows (these conventions may change):

- If only the day of the month is missing, the last day of the month will be used to replace the missing day
- If the day and month are missing or a date is completely missing, it will be considered as missing.

Missing and partial non-study medication domain dates will be imputed using the derivation algorithm described in 4.3.3 of BMS Non-Study Medication Domain Requirements Specification⁶.

For other partial/missing dates, the following conventions may be used:

- If only the day of the month is missing, the 15th of the month will be used to replace the missing day.
- If both the day and the month are missing, “July 1” will be used to replace the missing information.
- If a date is completely missing, it will be considered as missing.

The following conversion factors will be used to convert days to months or years: 1 month = 30.4375 days and 1 year = 365.25 days.

Duration (e.g. time from first diagnosis to first dosing date, duration of response, and time to response) will be calculated as follows:

Duration = (Last date - first date + 1)

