**Table 5.1-4: Follow-Up Assessments - All Subjects CA209627**

Procedure	Follow-Up Visits X01 (Day 35) ( $\pm 7$ Days) and X02 (Day 100) a ( $\pm 7$ Days) after last dose	Survival Follow-Up Visits b Every 12 weeks	Notes
Efficacy Assessments			
Radiographic Tumor Assessment	See notes		Only for subjects without progression and no longer on study therapy. If subject starts subsequent treatment, no assessment required  Subjects with a history of brain metastasis may have surveillance MRI approximately every 12 weeks or sooner if clinically indicated
Subject Status			
Survival Status	X	X	Every 3 months after X02; may be accomplished by visit or phone contact, to update survival information and assess subsequent anti-cancer therapy.

NOTES:

a Subjects must be followed for at least 100 days after last dose of study treatment. Follow-up visit #1 occurs approximately 35 days ( $\pm 7$  days) after the last dose or coinciding with the date of discontinuation ( $\pm 7$  days) if date of discontinuation is greater than 30 days after last dose. Follow-up visit #2 occurs approximately 100 days ( $\pm 7$  days) from last dose

b Survival Follow-up visits to occur every 3 months from Follow-up Visit 2. At the time of this request, each subject will be contacted to determine their survival status unless the subject has withdrawn consent for all contact. Vital signs not required if follow-up is performed via telephone contact.

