4.2.4 Overall Survival

OS is defined as time from the date of first dosing to the date of death. Subjects who did not die by the end of the study will be censored at the last known date alive. OS rate at 1 year is measured as the survival rate at 1 year from Kaplan-Meier curve of OS.

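### SAP 8 ignores a recorded year of death when the month is missing, so the imputed death can fall in an earlier year; day-missing progression dates also lack a lower bound, a rarer gap

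*SAP*

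**What the plan says.** SAP section 8 (Conventions) opens with "The following conventions may be used for imputing partial dates for analyses requiring dates" and then gives separate lists.

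**Death.** With the day missing: "If only the day of the month is missing, the 1st of the month will be used to replace the missing day". A guard follows: "The imputed date will be compared to the last known date alive and the maximum will be considered as the death date". With more missing: "If the month or the year is missing, the death date will be imputed as the last known date alive". A wholly missing date with a stated reason for death is treated the same way.

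**Progression.** With the day missing, the 1st of the month is used. If a complete death date exists, "The minimum of the imputed progression date and date of death will be considered as the date of progression". No other bound is given.

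**Other dates.** With day and month missing, the recorded year is kept and 1 July is used.

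The endpoints that use these dates are:
- SAP 4.2.4: "OS rate at 1 year is measured as the survival rate at 1 year from Kaplan-Meier curve of OS".
- SAP 4.1: a confirmed response needs two statuses at least 4 weeks apart, both before progression. For subjects treated beyond progression, best overall response (BOR) uses assessments only up to the initial RECIST 1.1 progression.
- SAP 7.5.3.1: progression at an unscheduled visit counts. One of its two definitions starts duration of response (DOR) at the first confirmed response.

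For late follow-up, Protocol Table 5.1-4 has "Survival Follow-up visits to occur every 3 months from Follow-up Visit 2", by visit or telephone. Protocol 3.6.1 and 3.6.2 allow vital status to come from public sources.

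**The concern.** An imputed date should agree with whatever part of the date was recorded. The day-missing death rule does: it takes the earliest date consistent with the recorded month and the last contact. The rule for other dates also respects a recorded year. The month-missing death rule treats a known year as if nothing were known. If the last contact was in an earlier calendar year, the imputed date is one that the record rules out. The error always shortens survival and can put a death on the wrong side of the 1-year mark.

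The progression rule has a related gap. Its date is limited from above by death but not from below by scans already read as free of progression. An imputed progression could then precede a confirming scan, which matters because SAP 4.1 requires confirmation before progression.

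**Working it through.** The documents give no figure to reproduce here, and no count of partial dates. The check applies the rules literally to constructed dates.

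**Death rule, one case**

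Inputs (constructed): first dose 15-Nov-2017; last known alive 20-Oct-2018; death recorded as 2019, month unknown. Time runs from first dose, as in SAP 4.2.4.

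- SAP date: 20-Oct-2018. Time from first dose = 365 − 26 = 339 days.
- Earliest date consistent with the record: 1-Jan-2019. Time = 365 + 47 = 412 days.
- Shortfall: at least 412 − 339 = 73 days.

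SAP 8 adds one day to durations, which gives 340 and 413. Either way the two dates lie on opposite sides of 1 year (365.25 days). If no one in the group is censored earlier, one such subject moves the 1-year estimate by 1/25 = 4 points in a group of 25. In a group of 14 (350 subjects over 25 groups) the shift is 1/14, about 7 points.

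**Death rule, how often the year is wrong**

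Assumptions: contacts are on time every 12 weeks (84 days), the gap from last contact to death is uniform over that interval, and deaths are spread evenly over the calendar year.

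- Share of year-only deaths with last contact in the previous year = mean gap / 365 = 42/365 = 11.5%.
- Enumerating every calendar day of 2017–2020 gives 11.6% for an 84-day interval, 12.6% for 91 days and 25.1% for 182 days (a missed contact).
- Mean shortfall against 1 January, when the year is wrong: 84²/3 ÷ (2 × 42) = 2352/84 = 28 days.

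**Death rule, how often the 1-year mark is crossed**

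Day 365 must also fall between the last contact and 1 January, an interval averaging 28 days. If last contacts are spread evenly over 2 years of follow-up (assumption), the share is 11.5% × 28/730 = 0.4% of year-only deaths. Over 1 year (assumption) it is 11.5% × 28/365 = 0.9%. Year-only deaths are themselves a subset of deaths.

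**Progression rule, one case**

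Inputs (constructed): first PR 10-Feb-2019; confirming PR 12-Mar-2019 (30 days later); progression on an unscheduled scan, true date 27-Mar-2019, recorded as March 2019 with the day unknown.

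- SAP date: 1-Mar-2019, 11 days before the confirming scan.
- DOR from confirmation (last − first + 1): −10 days, against a true 16.
- DOR from first PR: 20 days, against a true 46.
- Read literally, SAP 4.1 no longer finds a confirmation before progression.

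**Progression rule, reach**

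Scans are at Weeks 8, 16, 28 and then every 12 weeks, each ±5 days (Protocol 5.3.1). The shortest gap between scheduled scans is 112 − 56 − 10 = 46 days, so two of them never share a month and the share affected is 0%. An unscheduled or off-window scan is needed. Given one, and given a missing day, the share of start dates for which the imputed progression precedes confirmation is:

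| Days from confirming scan to progression scan | Share |
|---|---|
| 7 | 73.7% |
| 14 | 50.7% |
| 18 | 37.6% |
| 23 | 21.1% |
| 28 | 4.9% |
| 30 or more | 0% |

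An extra confirming scan 4 weeks after Week 8, followed by the Week 16 scan, gives gaps of 18 to 38 days.

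**The case against.** The best defence is that this hardly matters. One-year survival is secondary and reported descriptively by group; success and stopping rest on objective response rate (ORR). Earlier imputed deaths do not flatter the drug. Protocol 3.6.2 asks sites to obtain the date of death, and Protocol 3.6 lets the sponsor request extra survival contacts. If contacts really are on time, death is already confined to a window of about 12 weeks, so a year-only date mainly signals missed contact. All of this stands and limits the weight of the point. It does not justify overriding a recorded year.

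The permissive opening of SAP 8 is a weaker defence, because the death and progression lists themselves say what will be done. The term last known date alive is not defined in the available text, but that does not supply the missing bound.

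Two stronger readings are tempting and should be resisted:
- A reader might take the 12% as the share of deaths moved across the 1-year mark. It is the share of year-only deaths placed in the wrong calendar year. The crossing share is far smaller.
- A reader might infer that the progression rule threatens the primary endpoint in ordinary use. One lost responder would indeed cost 4 points of ORR at 25 subjects. But it takes an unscheduled or off-window scan in the same month as the confirming scan, with its day missing. Objective progression rests on imaging, and Protocol 5.3.1 requires unscheduled and outside scans to be collected, so the documents give no reason to expect this often.

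**Conclusion.** The death rule is wrong as written for one configuration: month missing, year recorded, last contact in an earlier calendar year. It then contradicts the record and shortens survival, in the example by at least 73 days and across the 1-year mark. If the year itself is missing, it contradicts nothing.

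The point is real but minor. The affected share is about 12% of year-only deaths under on-time contact and evenly spread deaths, more if contacts are missed. Roughly 0.4% to 0.9% of year-only deaths would cross 1 year under the stated spread assumptions. The total effect cannot be computed, because the number of partial dates is not given.

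The progression gap is real on the text but rarer still. It is a secondary point about making the derivation coherent and is no evidence of material bias in ORR.

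**What to change.** Amend SAP 8 as follows.

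1. **Death, month missing and year known:** impute the later of 1 January of that year and the last known date alive. Use the last known date alive by itself only when the year is missing.
2. **Progression, day missing:** take the later of the 1st of the recorded month and the day after the last evaluable non-progression assessment that preceded the initial progression assessment. Keep the result within the recorded month, then take the earlier of that date and death.

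The limits in item 2 are essential. Protocol 4.5.4 and 5.3.1 allow treatment and scanning beyond progression. A floor at any later non-progression scan could move progression past a post-progression response and let it into BOR, contrary to SAP 4.1. Scans after initial progression must not be used.

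The cost is a few sentences in the SAP and two lines of derivation code. No new data are needed. In the examples, the death moves to 1-Jan-2019 (day 412). The progression moves to 13-Mar-2019, which makes DOR from confirmation 2 days instead of −10.
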